9.4 Demographics and Baseline Characteristics

Patient characteristics will be summarized for the ITT/Safety and Evaluable Populations, and will include the following:

- Patient demographics (age, race, ethnicity)

- Baseline BPH/LUTS characteristics (prostate size by TRUS, PSA, Qmax, PVR)
- Clinically significant medical history
- Concurrent medical conditions
- Prior BPH/LUTS therapy

9.5 Efficacy Analyses

All efficacy analyses will be based on the ITT Population on the locked database after all patients have completed the 12 month follow-up visit or are lost to follow-up. If <15% of patients are excluded from the Evaluable Population, only the analyses of the ITT Population will be presented in the summary tables. If >15% of patients are excluded from the Evaluable Population, secondary efficacy analyses of the primary efficacy outcome will be performed on the Evaluable Population and included in the summary tables.

9.5.1 International Prostate Symptom Score (IPSS)

The primary efficacy outcome will be based on the IPSS. The IPSS is a frequent used, validated, 8 item (7 symptom burden questions and 1 quality of life question) instrument which can be serially performed to compare the progression of symptoms and their severity over months and years. Patients are asked to assess how often they have experienced the following 7 symptoms in the past month: incomplete emptying, frequency, intermittency, urgency, weak urine stream, straining and nocturia. The response categories range from 0=Not at all to 5=Almost always. The total IPSS score is calculated by summing the responses for the 7 symptom burden items. The eighth item is an assessment of patient quality of life due to LUTS and does not contribute to the IPSS score calculation.

Patients will be classified into one of 3 symptom severity categories based on their total IPSS score as follows:

- Mildly symptomatic: 0-7
- Moderately symptomatic: 8-19
- Severely symptomatic: 20-35

The IPSS total score will be summarized for the baseline, 1 month, 6 month and 12 month time points, including change from baseline. Change from baseline will be calculated as post baseline IPSS score minus baseline IPSS score. A negative value indicates symptom improvement. 95% confidence intervals will be calculated for the mean change from baseline to the post baseline time points. For informational purposes, IPSS scores will also be summarized separately for patients that receive unilateral and bilateral PAE if there are sufficient numbers in both groups.

The primary efficacy analysis will be the change in IPSS total score from baseline to 12 months post PAE for the ITT population. A Paired-Sample Wilcoxon Signed Rank Test will be used to assess the statistical significance of the change from baseline to 12 months post PAE. A secondary analysis of the proportion of patients who have improved by at least one IPSS symptom category (i.e., severe to moderate, severe to mild, or moderate to mild) from baseline to 12 months post PAE will also be performed. A 95% confidence interval will be calculated for the proportion. The proportion of patients improving at least 3 points on the IPSS total score at the 12 month time point will also be summarized and the corresponding 95% confidence interval will be calculated.

The single IPSS quality of life item will be summarized separately for baseline and all post baseline time points. Change from baseline will be calculated, including the corresponding 95% confidence interval for the mean change at each time point.

9.5.2 Prostate Size

Prostate size in cm³ as measured by TRUS will be summarized for the baseline, 1 month, 6 month and 12 month time points, including change and percent change from baseline. Change from baseline will be calculated as post baseline size minus baseline size. Percent change will be calculated as [change from baseline divided by baseline size] multiplied by 100. Negative changes from baseline indicate a decrease in

prostate size. The corresponding 95% confidence interval for the mean change and mean percent change will be presented for each time point.

9.5.3 Peak Urine Flow Rate (Qmax)

The Qmax determined by uroflowmetry will be summarized for the baseline, 1 month, 6 month and 12 month time points, including change from baseline. Change will be calculated as post baseline Qmax minus baseline Qmax. Positive values indicate an increase in flow rate. The corresponding 95% confidence interval for the mean change will be presented for each time point.

9.5.4 Post Void Residual Urine Volume (PVR)

The PVR determined by uroflowmetry will be summarized for the baseline, 1 month, 6 month and 12 month time points, including change from baseline. Change will be calculated as post baseline PVR minus baseline PVR. Negative values indicate a decrease in PVR. The corresponding 95% confidence interval for the mean change will be presented for each time point.

9.5.5 International Index of Erectile Function (IIEF)

The IIEF is a commonly used, validated instrument that consists of 15 items. Five subscales are calculated as follows:

- Erectile function (items 1-5, 15)
- Orgasmic function (9, 10)
- Sexual desire (11, 12)
- Intercourse satisfaction (6-8)
- Overall satisfaction (13, 14)

Each subscale will be summarized separately for the baseline, 1 month, 6 month and 12 month time points, including change from baseline. Change from baseline will be calculated as post baseline IIEF score minus baseline IIEF score. Positive values indicate an improvement in sexual function. 95% confidence intervals will be calculated for the mean change from baseline for each time point.

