3.2 Exclusion Criteria

Patients that meet any of the following exclusion criteria will not be eligible for this study.

1. History of prostate, bladder or rectal malignancy. Biopsy proven urethral cancer.
2. History of rectal disease
3. Neurogenic bladder disorder due to multiple sclerosis, Parkinson's disease, spinal cord injury, diabetes, etc., as demonstrated on urodynamic testing.
4. Detrusor muscle failure, urethral stenosis, or urinary obstruction due to causes other than BPH, as demonstrated on urodynamic testing
5. Bladder diverticula greater than 5 cm or bladder stones greater than 2 cm
6. Cystolithiasis within the past three months
7. Baseline serum creatinine greater than 1.8
8. Evidence of tortuous or atherosclerotic blood vessels
9. Presence of collateral vessel pathways potentially endangering normal territories during embolization that cannot be bypassed with the microcatheter
10. Active urinary tract infection, interstitial cystitis, or prostatitis within the last 5 years
11. Coagulation disturbances not normalized by medical treatment
12. Allergy to iodinated contrast agents not responsive to steroid premedication regimen
13. Previous radical pelvic or rectal surgery, or pelvic irradiation
14. Prior surgical prostate intervention
15. Treatment with beta-blocker, antihistamine, anticonvulsant, or antispasmodic medication within 1 week of treatment UNLESS there has been a stable voiding pattern while medicated with the drug(s) for 6 months
16. Use of prostate active medications, including alpha blockers, anti-cholinergics, androgens, anti-androgens, gonadotropins-releasing hormonal analogs, PDE5-inhibitors, 5-alpha reductase inhibitors within 2 months of intervention, unless the medication is necessary to avoid symptom exacerbation and disability, in this case medication should not be initiated or dose adjusted within 1 month of study enrollment and dose should not be adjusted during the study period
17. Interest in future fertility
18. Mental condition or disorder that interferes with participants' ability to provide written informed consent

19. Current severe or uncontrolled disease (metabolic, hematologic, renal, hepatic, pulmonary, neurologic, cardiac, infectious or gastrointestinal) that in the Investigator's judgment makes the patient unsuitable for trial inclusion due to increased risk of complications
20. Known immunosuppression
21. Life expectancy less than 6 months

4. Study Design

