5.1 Visit -1: Screening/Baseline (within 4 weeks of PAE)

Patients meeting all of the inclusion and none of the exclusion criteria listed in Section 3 are eligible for participation in this study.

Prior to enrollment, each patient will have the following assessments performed:

- Obtain written informed consent
- Medical history, including demographics
- Physical exam including vital signs
- Recording of concurrent medical conditions
- IPSS and IIEF questionnaires
- Transrectal ultrasound (TRUS) of the prostate
- Transabdominal ultrasound (TAUS) of the bladder
- Uroflowmetry to assess Qmax
- Laboratory evaluations, including a complete blood count (CBC), complete metabolic panel (CMP), urinalysis, urine culture, and prostate specific antigen (PSA)
- Preprocedural CT angiography of the pelvis
- Prostate biopsy, if indicated by protocol
- Recording of concomitant medications
- Anoscopy if clinically indicated for evaluation of suspected rectal disease

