5.2 Visit 1: Prostate Artery Embolization (PAE)

The PAE procedure will be performed within 4 weeks of baseline prostate ultrasound. PAE with Embosphere Microspheres will be performed according to the technical procedure provided in Appendix C.

Treatment data recorded will include the following:

- Total fluoroscopy time
- Total radiation dose
- Number and origins of arterial supply
- Volume and size of embolic material delivered
- Evidence of collateral blood supply
- Duration of hospitalization
- Sedative medications administered
- Patient pain score before and after procedure

- Procedure adverse events

5.3 Visits 2, 3, 4: 1 Month, 6 Months, 12 Months (4 weeks, 24, 52 ± 2 weeks post PAE)

Patients will have the following assessments performed:

- Physical exam, including vital signs
- IPSS and IIEF questionnaires
- TRUS of the prostate
- TAUS of the bladder
- Laboratory evaluations, including a complete blood count (CBC), complete metabolic panel (CMP), urinalysis, urine culture, and prostate specific antigen (PSA)
- Uroflowmetry to assess Qmax
- Cystoscopy, if clinically indicated
- Proctoscopy, if clinically indicated
- Review of concomitant medications and adverse events

Patients who are unable or unwilling to return for follow-up will be contacted by telephone, email, or mail to administer the IPSS and IIEF questionnaires, and to report any new treatments for BPH and/or LUTS.

5.4 Visit 5 (Long Term Follow-Up): 24 Months (104 ± 2 weeks post PAE)

Patients will have the following assessments performed:

- Physical exam, including vital signs
- IPSS and IIEF questionnaires
- TRUS of the prostate
- TAUS of the bladder
- Laboratory evaluations, including a complete blood count (CBC), complete metabolic panel (CMP), urinalysis, urine culture, and prostate specific antigen (PSA)
- Uroflowmetry to assess Qmax

Patients who are unable or unwilling to return for follow-up will be contacted by telephone, email, or mail to administer the IPSS and IIEF questionnaires, and to report any new treatments for BPH and/or LUTS.

6. Withdrawal of Patients

Patients will be informed that they have the right to withdraw from the study at any time for any reason, without prejudice to their medical care. The Investigator also has the right to withdraw patient from the study for any of the following reasons:

- Adverse event
- Concurrent medical condition
- Patient unwillingness to comply with study requirements
- Patient death
- Other Investigator decision

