9.6.5 Concomitant Medications

Concomitant medications data will be presented in the data listings.

9.7 24 Month Follow-Up Data

The data described in section 5.4 will be collected at the 24 month follow-up visit.

Data collected during the 24 month follow visit will be summarized separately from the data collected during the initial 12 month post PAE study period. All 24 month follow-up visit data recorded on the CRF will be included in the data listings. Select 24 month follow-up data may summarized, including change from baseline values, where applicable.

10. Records, Confidentiality and Data Monitoring

Each patient will be identified by study ID number only in the trial records. Study data will be recorded on pre-printed CRFs. Monitoring of study data recorded on source documents and reported on study CRFs will be conducted for all patients to ensure accuracy and completeness.

11. Quality Control and Assurance

It will be the responsibility of the Principal Investigator to ensure that data collection and reporting is complete and accurate.

12. Good Clinical Practice

This investigation will be conducted in accordance with the International Conference on Harmonization (ICH) E6 for Good Clinical Practice (GCP): Consolidated Guidance and all appropriate regulatory requirements. The Investigator will be thoroughly familiar with the appropriate use of the treatment procedure as described in the protocol. Essential clinical documents will be maintained to demonstrate the validity of the study and the integrity of the data collected. Master files will be established by the site personnel at the beginning of the study, maintained for the duration of the trial and retained according to all appropriate regulations.

13. Ethical Considerations

The study will be conducted in accordance with ethical principles founded in the Declaration of Helsinki. The Institutional Review Board (IRB) will review all appropriate study documentation, including the protocol, informed consent and any advertisements that will be used for the study, in order to safeguard the rights, safety and well-being of the patients. The study will only be conducted once IRB approval has been obtained. Safety updates, annual progress reports and any revisions to these documents will be provided to the IRB by the Principal Investigator as required by regulations.

14. Patient Information and Informed Consent

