Appendix E: International Index of Erectile Function (IIEF)

INTERNATIONAL INDEX OF ERECTILE FUNCTION (IIEF) QUESTIONNAIRE						
Please circle the appropriate number to respond to each question.						
	0	1	2	3	4	5
1. Over the past 4 weeks, how often were you able to get an erection during sexual activity?	No sexual activity	Almost never/ never	A few times (much less than half the time)	Sometimes (about half the time)	Most times (much more than half the time)	Almost Always/ Always
2. Over the past 4 weeks, when you had erections with sexual stimulation, how often were your erections hard enough for penetration?	No sexual activity	Almost never/ never	A few times (much less than half the time)	Sometimes (about half the time)	Most times (much more than half the time)	Almost Always/ Always
3. Over the past 4 weeks, when you attempted sexual intercourse, how often were you able to penetrate (enter) your partner?	Did not attempt intercourse	Almost never/ never	A few times (much less than half the time)	Sometimes (about half the time)	Most times (much more than half the time)	Almost Always/ Always
4. Over the past 4 weeks, during sexual intercourse, how often were you able to maintain your erection after you had penetrated (entered) your partner?	Did not attempt intercourse	Almost never/ never	A few times (much less than half the time)	Sometimes (about half the time)	Most times (much more than half the time)	Almost Always/ Always
5. Over the past 4 weeks, during sexual intercourse, how difficult was it to maintain your erection to completion of intercourse?	Did not attempt intercourse	Extremely difficult	Very difficult	Difficult	Slightly difficult	Not difficult
6. Over the past 4 weeks, how many times have you attempted sexual intercourse?	No attempts	One to two attempts	Three to four attempts	Five to six attempts	Seven to ten attempts	Eleven plus attempts
7. Over the past 4 weeks, when you attempted sexual intercourse, how often was it satisfactory to you?	Did not attempt intercourse	Almost never/ never	A few times (much less than half the time)	Sometimes (about half the time)	Most times (much more than half the time)	Almost Always/ Always
8. Over the past 4 weeks, how much have you enjoyed sexual intercourse?	No intercourse	No enjoyment	Not very enjoyable	Fairly enjoyable	Highly enjoyable	Very highly enjoyable

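### The IIEF change from baseline takes no account of PDE5 inhibitors started or resumed after PAE, although exclusion 16 makes the baseline off-drug for any man who stopped one

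*Combined protocol and SAP*

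**What the plan says.** **Eligibility.** Section 3.2, item 16, lists among the excluded drugs "PDE5-inhibitors, 5-alpha reductase inhibitors within 2 months of intervention, unless the medication is necessary to avoid symptom exacerbation and disability". For men kept on a drug under that exception, the item sets a stability condition before entry: "in this case medication should not be initiated or dose adjusted within 1 month of study enrollment". A further condition applies to the same men after entry: "dose should not be adjusted during the study period". Both conditions attach to the exception group. No rule covers a man who stopped, or who never used such a drug, and then takes one after PAE.

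**Measurement.** The baseline visit falls within 4 weeks before PAE (section 5.1). The IIEF asks about the preceding 4 weeks, for example "Over the past 4 weeks, how often were you able to get an erection during sexual activity" (Appendix E). It is repeated at months 1, 6, 12 and 24.

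**Analysis.** Section 9.5.5 summarises each subscale to month 12 as the post-baseline score minus the baseline score, and states "Positive values indicate an improvement in sexual function". It has no drug-status flag, split or sensitivity analysis, and the missing-data rules in 9.5.7 add none. Section 9.6.5 says "Concomitant medications data will be presented in the data listings" and goes no further.

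**Collection.** Sections 5.1 and 5.3 and Appendix A schedule recording of concomitant medications at baseline and months 1, 6 and 12; Appendix A also marks the treatment visit. A man who cannot or will not attend is contacted remotely "to administer the IPSS and IIEF questionnaires, and to report any new treatments for BPH and/or LUTS" (5.3 and 5.4). For month 24, section 4 lists medication and adverse event reviews, whereas section 5.4 and Appendix A do not.

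**The concern.** Sexual function is secondary objective 8, and erectile dysfunction is a named risk of PAE (section 7.1 and Appendix C). The IIEF summary therefore also serves as a safety signal.

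There are two routes to error. A man who stopped a PDE5 inhibitor for the trial and resumes it afterwards can show a gain that reflects the drug. A man whose erections worsen after PAE and who then starts a drug can show little or no loss. Both push the mean change in the favourable direction, and a single-arm study has no comparison group in which the same drift would be visible. Last observation carried forward (9.5.7) can also carry an on-drug score to a later time point.

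**Working it through.** The plan has no figure to reproduce. Section 9.2 states that no formal sample size calculation was made, and no IIEF effect, standard deviation (SD) or count of PDE5-inhibitor users is given. Two checks can be made.

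**1. Is the baseline IIEF wholly off-drug for a man who stopped under the rule?**
- Drug-free period before PAE: 2 months = 2 × 365.25/12 ≈ 61 days, so from about day −61.
- Earliest baseline visit: day −28 (section 5.1).
- Start of the 4-week recall for that visit: −28 − 28 = day −56 (Appendix E).
- Margin: 61 − 56 ≈ 5 days.

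The whole recall period lies inside the drug-free period even at the earliest permitted visit. Section 9.1 takes the value closest to the procedure as baseline, which can only widen the margin.

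**2. How far could the mean move?**
- From the documents: n = 20 (section 4). The erectile function subscale uses items 1–5 (0–5 each) and item 15 (1–5), so it runs from 5 × 0 + 1 = 1 to 6 × 5 = 30.
- Assumed, not in the documents: k men start or resume (2, 4 or 6), and each gains g points (3 to 8).
- Shift in mean change = k × g / 20.

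| k | g = 3 | g = 8 |
|---|---|---|
| 2 | 2 × 3/20 = +0.3 | 2 × 8/20 = +0.8 |
| 4 | 4 × 3/20 = +0.6 | 4 × 8/20 = +1.6 |
| 6 | 6 × 3/20 = +0.9 | 6 × 8/20 = +2.4 |

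If every user qualifies for the exception, no one resumes and that part of k is zero. New starters after PAE could still contribute.

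**Masking example (assumed numbers).** Three men lose 6 points: −3 × 6/20 = −0.9. Three others resume a drug and gain 6 points: +3 × 6/20 = +0.9. The reported mean is 0.0.

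**Scale against sampling error.** The 95% confidence interval half-width is t(0.975, 19) × SD/√20. At assumed SDs of 5, 7 and 9 it is 2.3, 3.3 and 4.2 points. Nearly all the shifts above are smaller than this.

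**The case against.** Several counter-arguments have force.

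- **Sign convention.** The sentence on positive values says which way the scale runs, as similar sentences do for IPSS, Qmax and PVR. A reader might infer that the plan credits any gain to PAE. It does not say so, and limited attribution affects every endpoint in an uncontrolled study. What stands is that a drug effect on this endpoint is foreseeable and the summary does not separate it.
- **Number affected.** A reader might infer that item 16 takes most users off the drug. The documents give no count of users, and the exception is a matter of judgement, so the share could be anywhere from none to all.
- **Hidden harm.** A reader might infer that erectile harm would vanish from the trial. It need not. Adverse events are recorded from PAE to 12 months (7.2) with relationship and treatment required (7.1), and are summarised by Preferred Term (9.6.1). This safeguard stands but is partial, because a man whose function is restored by a drug may report nothing.
- **Data mostly exist.** For attended visits to month 12, drug use is recorded and could be lined up against the IIEF in the listings. That is correct: there the gap is in the summary, not in collection. It becomes a collection gap for remote contacts. At month 24 a plain omission is tempting to infer, but section 4 does list a medication review at that visit. The fault is a conflict between sections. Month 24 also lies outside 9.5.5, and section 9.7 makes its summary optional.
- **Small relative to the interval.** This is true under nearly all the assumptions shown, but the interval measures sampling error around a mean that may already be shifted.
- **Selection.** Restricting to men with unchanged drug status removes those who start a drug because PAE harmed them. This objection stands and shapes the fix.

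**Conclusion.** The concern holds in a limited form. For any man who stops a PDE5 inhibitor under item 16, the baseline IIEF is off-drug by the protocol's own timing. Later use is neither addressed nor accounted for in 9.5.5, so the mean change can include drug effect and can mask erectile loss within that summary.

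The shift of +0.3 to +2.4 points rests wholly on assumed numbers of men and assumed gains; the documents cannot narrow it. The point concerns a secondary outcome with no planned hypothesis test and leaves the primary IPSS analysis untouched. It merits correction because the endpoint bears on a named risk, and because drug status not asked about at remote contacts or month 24 may not be reliably recoverable later.

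**What to change.** 1. **Section 9.5.5:** flag each IIEF as on or off PDE5 inhibitor during its 4-week recall period, using the medication review. Keep the all-men summary as the main result. Beside it report (a) the number who started or resumed after PAE, (b) the erectile function change in men whose status matches baseline, and (c) the same change in starters and resumers. State that (b) conditions on a post-treatment event and can look favourable if men start a drug because of PAE-related harm, so it should not be presented alone.
2. **Sections 5.3 and 5.4:** add drugs for erectile function to the treatments asked about at remote contact.
3. **Month 24:** reconcile section 4, which lists medication and adverse event reviews at that visit, with section 5.4 and Appendix A, which do not, so that drug status is known for the month-24 IIEF.

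The cost is one extra question at remote contact and a few table rows based on small numbers. No view is taken on whether starting or resuming a drug should be allowed.

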2.2 Secondary Objectives

The secondary objectives of this investigation are to assess the following outcomes, compared to baseline values when appropriate:

1. PAE-related adverse events
2. Overall adverse events
3. Prostate volume as determined by transrectal ultrasound
4. Serum prostate specific antigen (PSA) level
5. Post void residual volume (PVR) as determined by transabdominal ultrasound
6. Post void residual urinary volume (PVR) as determined by uroflowmetry
7. Peak urine flow rate (Qmax) as determined by uroflowmetry
8. Sexual function as determined by the International Index of Erectile Function (IIEF)

3. Patient Population

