- For PAE: Hematospermia, hemorrhage, injury to the bladder (including the bladder neck, ureteral orifice or trigone), impact on future fertility, vasospasm, rectorrhagia, inguinal hematoma, bladder/bladder neck ischemia and necrosis leading to bladder resection, balanitis, erectile dysfunction, rectal ischemia, rectal injury, allergic reaction to Embosphere Microspheres or contrast agent, radiation exposure, vascular perforation, need for subsequent surgery to repair non-target ischemia, and sensory abnormality

Serious Adverse Event: A serious adverse event (SAE) is any adverse event, occurring at any dose and regardless of causality that:

- Results in death
- Is life-threatening, such that the patient was at immediate risk of death from the event as it occurred (i.e., it does not include a reaction which hypothetically might have caused death had it occurred in a more severe form)
- Requires inpatient hospitalization or prolongation of existing hospitalization. Hospital admissions and/or surgical operations scheduled to occur during the study period but planned prior to study entry are not considered AEs if the illness or disease existed before the patient was enrolled in the study, provided that the patient's condition does not deteriorate in an unexpected manner during the study (e.g., surgical procedure performed earlier than planned)
- Results in persistent or significant disability/incapacity, such that the patient experiences a substantial disruption of their ability to conduct normal life functions

- Is an important medical event as determined by the Investigator. An important medical event is an event that may not result in death, be life-threatening, or require hospitalization, but may be considered an SAE when, based upon appropriate medical judgment, it may jeopardize the patient and may require medical or surgical intervention to prevent one of the outcomes listed above. Examples of such medical events include allergic bronchospasm requiring intensive treatment in an emergency room or at home, blood dyscrasias or convulsions that do not result in inpatient hospitalization, or the development of drug dependency or drug abuse.

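### For three IIEF subscales, inactivity scores 0 and all treated men are averaged, so men inactive at baseline can show little or no fall and a change in activity counts as a change in function

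*Combined protocol and SAP*

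**What the plan says.** Sexual function measured by the IIEF is the eighth secondary objective (section 2.2). Section 9.5.5 forms five subscales from the 15 items, takes follow-up minus baseline for each, and reports the mean change with a 95% confidence interval at 1, 6 and 12 months. It interprets the result with the sentence "Positive values indicate an improvement in sexual function".

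The analysis population is every man who undergoes PAE (sections 9.3.1 and 9.5). Eligibility covers men over 50 and under 85 and does not ask for sexual activity (sections 3.1 and 3.2).

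In Appendix E, items 1 to 10 each have a 0 answer that records inactivity. Items 3, 4, 5 and 7, for example, give 0 for "Did not attempt intercourse". Items 11 to 15 run from 1 to 5 and have no such answer.

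Section 9.5.7 gives rules for missing values and outliers. Neither it nor 9.5.5 says how a 0 that means inactivity is to be handled. Section 7.1 names the sexual harm of interest among the risks of PAE: "balanitis, erectile dysfunction, rectal ischemia, rectal injury".

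**The concern.** A 0 on items 1 to 10 is not a graded answer about function. It says that there was nothing to rate, and it sits below the lowest answer open to a man who was active. Two things follow when such scores enter a mean change.

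First, a man already at the floor has little or no room to get worse, so he pulls an average loss towards zero. Second, a man who stops or starts activity because of a partner, an illness or recovery from the procedure moves many points, and the plan's sign rule counts that as function lost or gained. Month 1 is the most exposed visit: the items ask about the past 4 weeks and the visit falls at 4 weeks, plus or minus 2.

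At stake is the interpretation of secondary objective 8, for a procedure that lists erectile dysfunction as a risk. The study has a single arm of 20, so no control group shows how activity drifts by itself, and each man who switches carries weight.

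**Working it through.** The plan has no sample size calculation and no IIEF target, so there is no figure of its own to reproduce.

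**Inputs.** Subscale items are from section 9.5.5, item scores from Appendix E, and N = 20 from section 9.2. The share of inactive men and the size of any true change are not in the documents; the values in steps 2 to 4 are assumptions.

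**Step 1: room to fall.** Add the item minima and maxima. For a fully inactive man, set items 1 to 10 to 0. His largest fall is his highest possible score minus the subscale minimum.

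| Subscale (items) | Possible range | Range if fully inactive | Largest fall from an inactive baseline |
|---|---|---|---|
| Erectile (1-5, 15) | 1-30 | 1-5 | 5 - 1 = 4 |
| Orgasmic (9, 10) | 0-10 | 0 | 0 |
| Intercourse satisfaction (6-8) | 0-15 | 0 | 0 |
| Sexual desire (11, 12) | 2-10 | 2-10 | 10 - 2 = 8 |
| Overall satisfaction (13, 14) | 2-10 | 2-10 | 10 - 2 = 8 |

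The first three subscales are affected and the last two are not. The 4 points on the erectile subscale come from item 15 alone; a man starting at 30 could fall by 29.

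Inactivity is not one state. A man with sexual activity but no intercourse can still score on items 1, 2 and 15, up to 3 x 5 = 15 on the erectile subscale, and up to 10 on the orgasmic subscale. The 1-5 range holds only for complete inactivity.

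**Step 2: dilution.** Let k of 20 men be inactive at both visits with no change, and let each of the others lose 5 erectile points. The mean over all men is -5 x (20 - k)/20:

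- k = 4: -4.0
- k = 6: -3.5
- k = 8: -3.0
- k = 10: -2.5

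Among men active at baseline the mean is -5.0 in every case.

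**Step 3: one man switching.** A man who scores 30, stops all activity and still answers 5 on item 15 goes to 5. His change of -25 moves the mean of 20 by -25/20 = -1.25. The reverse switch moves it by +1.25.

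**Step 4: both together.** Suppose 6 men are inactive at baseline, the 14 active men each lose 5, and 4 of the 6 resume with +20 each. The mean is (-5 x 14 + 20 x 4)/20 = 10/20 = +0.5, which the sign rule calls improvement. This is a constructed case. It shows that the sign can reverse, not that it is likely to.

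**The case against.** The best reply has four parts.

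- **A mean over all treated men is a legitimate summary.** The quoted sentence is a scoring convention like those for IPSS, Qmax and PVR, and the IIEF result is descriptive, with no test attached. This stands. It is why the planned summary should be kept and why the point is minor.
- **Other provisions show part of the picture.** Section 9.1 gives the median, minimum and maximum and lists all CRF data. Section 9.5.7 investigates outliers and requires those that affect the summaries to be discussed. With 20 men, a reader of the listings could find the switches. This also stands, but none of these provisions separates inactivity from dysfunction in a reported summary, and a man at the floor at both visits is not an outlier.
- **Erectile harm can be reported as an adverse event.** Sections 7.1 and 9.6.1 provide for this. It means that detection of harm does not rest on the IIEF alone, but it does not correct the IIEF mean.
- **The inactive share is unknown.** That is so, and the sizes above are illustrations only.

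A reader might also infer that a man inactive at baseline cannot show sexual harm anywhere on the IIEF. Appendix E does not support this: desire and overall satisfaction keep their full range, and erectile function can still fall through item 15. Nor does the point dispute the instrument or its standard scoring.

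**Conclusion.** The point holds for the erectile, orgasmic and intercourse satisfaction subscales only. The limits of 4, 0 and 0 points from a fully inactive baseline follow from the form itself and need no assumption. The dilution of a 5-point fall to between 4.0 and 2.5 assumes that 4 to 10 of 20 men are inactive at both visits and do not change. The shift of 1.25 assumes one man going from 30 to 5, or the reverse.

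It would go too far to say that the planned mean will conceal harm, or that one switch overwhelms the result. The documents give no share of inactive men, and a shift of 1.25 is smaller than the diluted effects of 2.5 to 4.0. This is a cheap improvement to a secondary outcome; the primary IPSS analysis is untouched.

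**What to change.** Keep the all-men summary in section 9.5.5. Before database lock, add the following for the three affected subscales.

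1. The change among men active at baseline, with activity defined per subscale: erectile, items 1 to 5 all non-zero; orgasmic, items 9 and 10 non-zero; intercourse satisfaction, item 6 non-zero. One rule for all three would not do. Requiring intercourse attempts for the orgasmic subscale would discard valid answers, because items 9 and 10 also cover stimulation without intercourse.
2. No restriction on activity at follow-up in this summary. A subset active at both visits would drop a man who stopped because treatment impaired his function, and so could hide the harm being sought.
3. At each visit, the number of men inactive, the number who went from active to inactive, and the number who went the other way.

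Sexual desire and overall satisfaction stay as planned.

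The cost is one extra table from data already collected. The subset is smaller: at the same standard deviation, going from 20 men to 16 or 10 raises the standard error by a factor of sqrt(20/16) = 1.12 or sqrt(20/10) = 1.41. The erectile subset may be smaller still, since its rule also leaves out men active without intercourse.

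Men who stop activity still count as a fall, with more weight: a change of -25 moves a mean of 16 by 25/16 = 1.56 and a mean of 10 by 2.5. The shift counts must therefore be read beside the subset mean, and they do not give the reason for stopping.
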